9.3 File Management at the Trial Site

The investigator will ensure that the trial site file is maintained in accordance with Section 8 of the ICH GCP Guideline E6 and as required by applicable local regulations.

Protocol 031-201-00301

The investigator/institution will take measures to prevent accidental or premature destruction of these documents.

9.4 Records Retention at the Trial Site

Food and Drug Administration regulations require all investigators participating in clinical drug trials to maintain detailed clinical data for one of the following periods:

- A period of at least 2 years after the date on which a New Drug Application is approved by the FDA.
- A period of 2 years after the sponsor has notified the FDA that investigation with this drug is discontinued.

The investigator must not dispose of any records relevant to this trial without either (1) written permission from the sponsor or (2) provision of an opportunity for sponsor to collect such records. The investigator will be responsible to maintain adequate and accurate electronic or hard copy source documents of all observations and data generated during this trial including any data clarification forms received from the sponsor. Such documentation is subject to inspection by the sponsor and relevant regulatory authorities. If the investigator withdraws from the trial (eg, due to relocation or retirement), all trial-related records should be transferred to a mutually agreed-upon designee within a sponsor-specified timeframe. Notice of such transfer will be given to the sponsor in writing.

10 Quality Control and Quality Assurance

10.1 Monitoring

The sponsor has ethical, legal, and scientific obligations to follow this trial in accordance with established research principles, the ICH E6 GCP: Consolidated Guidance, and applicable regulatory requirements and local laws. As part of a concerted effort to fulfill these obligations (maintain current personal knowledge of the progress of the trial), the sponsor's monitors will visit the site during the trial, as well as communicate frequently via telephone, email, and written communications. In addition, all investigators and clinical site personnel will undergo initial and ongoing training for this particular trial, and this training will be clearly documented.

10.2 Auditing

The sponsor's Quality Assurance Unit (or representative) may conduct trial site audits. Audits will include, but are not limited to, Abilify MyCite supply, presence of required

Protocol 031-201-00301

documents, the informed consent process, and comparison of case report forms (CRFs) with source documents. The investigator agrees to participate with audits.

Regulatory authorities may inspect the investigator site during or after the trial. The investigator will cooperate with such inspections and will contact the sponsor immediately if such an inspection occurs.

11 Ethics and Responsibility

This trial must be conducted in compliance with the protocol, FDA regulations, ICH GCP Guideline (E6), international ethical principles derived from the Declaration of Helsinki and Council for International Organizations of Medical Science (CIOMS) guidelines, and applicable local laws and regulations. Each trial site will seek approval/favorable opinion by an IRB according to regional requirements, and the investigator will provide that documentation to the sponsor. The IRB will evaluate the ethical, scientific and medical appropriateness of the trial. Further, in preparing and handling CRFs, the investigator, sub-investigator and their staff will take measures to ensure adequate care in protecting subject privacy. To this end, a subject number and subject identification code will be used to identify each subject.

Financial aspects, subject insurance and the publication policy for the trial will be documented in the agreement between the sponsor and the investigator.

12 Confidentiality

All information generated in this trial will be considered confidential and will not be disclosed to anyone not directly concerned with the trial without the sponsor's prior written permission. Subject confidentiality requirements of the region(s) where the trial is conducted will be met. However, authorized regulatory officials and sponsor personnel (or their representatives) may be allowed full access to inspect and copy the records, consistent with local requirements. All IMPs, subject bodily fluids, and/or other materials collected shall be used solely in accordance with this protocol, unless otherwise agreed to in writing by the sponsor.

Subjects will be identified only by unique subject numbers in CRFs. If further subject identification is required, subjects' full names may be made known to a regulatory agency or other authorized officials if necessary, subject to local regulations.

Protocol 031-201-00301

13 Amendment Policy

The investigator will not make any changes to this protocol without the sponsor's prior written consent and subsequent approval/favorable opinion by the IRB. Any permanent change to the protocol, whether an overall change or a change for specific trial site(s), must be handled as a protocol amendment. Any amendment will be written by the sponsor. Each amendment will be submitted to the IRB, as required by local regulations. Except for "administrative" or "non-substantial" amendments, investigators will wait for IRB approval/favorable opinion of the amended protocol before implementing the change(s). Administrative amendments are defined as having no effect on the safety of subjects, conduct or management of the trial, trial design, or the quality or safety of Abilify MyCite used in the trial. A protocol change intended to eliminate an apparent immediate hazard to subjects should be implemented immediately after agreement by the sponsor and investigator, followed by IRB notification within local applicable timelines. The sponsor will submit protocol amendments to the applicable regulatory agencies within local applicable timelines.

When the IRB, investigators, and/or the sponsor conclude that the protocol amendment substantially alters the trial design and/or increases the potential risk to the subject, the currently approved written ICF will require similar modification. In such cases, after approval/favorable opinion of the new ICF by the IRB, repeat written informed consent will be obtained from subjects enrolled in the trial before expecting continued participation and before the amendment-specified changes in the trial are implemented.

14 Publication Authorship Requirements

Authorship for any Otsuka-sponsored publications resulting from the conduct of this trial will be based on International Committee of Medical Journal Editors (ICMJE) authorship criteria (<http://www.icmje.org/recommendations>). According to ICMJE guidelines, one may be considered an author only if the following criteria are met:

1. Substantial contributions to the conception or design of the work; or the acquisition, analysis, or interpretation of data for the work; AND

Appendix 3 Abilify MyCite Contents

Abilify MyCite Contents	
Abilify MyCite Component	Description
Aripiprazole + IEM	Aripiprazole tablet with sensor will be dispensed to the subjects during the trial. Tablets will be taken as prescribed by the healthcare provider, with approximately 120 mL of water.
Patch	Patches will be dispensed to a subject for use. The current Abilify MyCite DW5 patch is a one-piece unit. The patch has an adhesive backing that adheres to the user's body and requires the patch to be changed approximately once per week. The updated patch (RW2) is made up of two parts; (1) a data pod and (2) an adhesive strip. As with the DW5 patch, the adhesive strip needs to be replaced approximately once per week, but the data pod is for extended use and needs to be inserted into the adhesive strip whenever it is changed. The updated patch was designed to eliminate the step of having to press a button to pair the patch with the app. The data pod only needs to be paired with the app on initial use and does so without the need to press a button, unlike the DW5 patch that needed to be paired with every application of a new patch. The new pod/strip combination also allows for an expanded area for patch placement.
Computing Device & Accessories	Subjects will use their own smartphone and required accessories. Subjects will be requested to carry their smartphone with them as much as possible and to plug in the device at a dedicated location at home where they could have easy and frequent access when not being carried. The preferred location is on a nightstand or a location immediately adjacent to where the subject sleeps.
Abilify MyCite Reference Guide	A printed reference guide will provide explicit directions for normal use and troubleshooting.

Protocol 031-201-00301

Appendix 4 Protocol Amendment

Amendment Number: 1
Issue Date: 11 Feb 2019

PURPOSE:

The protocol was amended to revise the secondary and exploratory endpoints and to add an exploratory endpoint for the [REDACTED]. In addition, minor clarifications to the monthly assessments and corresponding trial days, assessment window, endpoints, inclusion and exclusion criteria, schedule of assessments, and ECG assessment language were incorporated.

BACKGROUND:

The intention of this protocol amendment was to revise the trial endpoints to better match the intended study objectives. These changes to clinical trial protocol 031-201-00301, issued 04 Jan 2019, are listed below in detail.

MODIFICATIONS TO PROTOCOL:

Sectional Revisions:

Description of Change	Sections Affected by Change
Clarified assessment window of - 3/ + 2 days for Months 1 through 6 globally	Global change
Clarified monthly assessments will follow a 28-day schedule and revised study days accordingly	Protocol synopsis Section 3.1 Type/Design of Trial Figure 3.1-1 Trial Design Schematic Section 3.5.3 Exploratory Endpoints Table 3.7-1 Schedule of Assessments Section 3.7.1.3 Prospective Phase (6 Months)
Clarified in the inclusion criteria that caregiver support may be utilized throughout the trial and that the caregiver/support person will be asked (where applicable) to provide feedback via the Caregiver Involvement Scale	Protocol synopsis Table 3.4.2-1 Inclusion Criteria
Removed exclusion criterion #4 regarding hospitalization during the screening period	Protocol synopsis Table 3.4.3-1 Exclusion Criteria
Clarified the secondary endpoint for the trial	Protocol synopsis Section 3.5.2 Secondary Endpoint Section 7.4.2 Secondary Endpoint Analysis
Revised several secondary endpoints to exploratory endpoints and clarified the exploratory endpoint analysis for the [REDACTED]	Protocol synopsis Section 3.5.3 Exploratory Endpoints Section 7.4.3 Exploratory Endpoint Analysis
Removed Abilify MyCite product, supplies, and patch dispensation at Month 6/ET	Table 3.7-1 Schedule of Assessments Section 3.7.1.3.5 Month 6/Early Termination Visit
Clarified language regarding ECG assessments	Section 3.7.3.4 Electrocardiogram Assessments

Protocol 031-201-00301

ADDITIONAL RISK TO THE SUBJECT:

There is no additional risk to the subjects.

Protocol 031-201-00301

Agreement

The objective of this study is to compare inpatient psychiatric hospitalization rates (proportion of subjects with ≥ 1 inpatient psychiatric hospitalizations) between the retrospective period (Months 1 to 3) while subjects are on oral standard-of-care antipsychotic treatment and the prospective period (Months 1 to 3) after the subjects switch to Abilify MyCite.

3 Study Design

This is a phase 3b, open-label, prospective, clinical trial designed to assess the difference between inpatient psychiatric hospitalization rates in subjects on oral standard-of-care antipsychotic treatment(s) for a period of 6 months followed by a switch to Abilify MyCite for a period of 3 months (Months 1 to 3). At the Month 3 visit, the investigator should decide if subjects will continue on Abilify MyCite for an additional 3 months (Months 4 to 6) or switch to a standard-of-care treatment (eg, oral atypical antipsychotics or a long acting injectable [LAI]) for the duration of treatment.

This trial will include male and female subjects who are 18 to 65 years of age, inclusive, with a diagnosis of schizophrenia according to Diagnostic and Statistical Manual of Mental Disorders, Fifth Edition (DSM-5) criteria. Subjects must have had at least 1 inpatient psychiatric hospitalization within 4 years (48 months) and must have been prescribed oral antipsychotics for at least 6 months or longer prior to screening.

Subjects will enter a screening period (up to 45 days). If deemed eligible to participate, subjects will enter an open-label Abilify MyCite treatment prospective phase for up to 6 months. A schematic of the study design is provided in [Figure 3.1-1](#).

3.1 Type/Design of the Trial

Oral Standard-of-Care Antipsychotic Treatment(s) (Retrospective Phase)

To be eligible for trial participation, subjects must have been prescribed oral antipsychotic standard-of-care pharmacotherapy for at least 6 months or longer, with evidence of prescription (i.e., pharmacy records) during the retrospective phase and prior

Protocol 31-201-301 Interim Analysis Plan

to screening. Subjects administered antipsychotics other than aripiprazole must cross-titrate onto oral aripiprazole during the screening period at the discretion of the investigator to be eligible for trial participation.

Screening

After providing informed consent, subjects will enter the 45-day (Days -45 to -1; approximately 6 weeks) screening period to determine if they are eligible to enter the Abilify MyCite treatment (prospective) phase. The subject's past psychiatric history for the 6 months prior to screening must be available, inclusive of a comprehensive review of all psychiatric hospitalizations and interventions (psychiatric only).

As safety of the subject dictates, 2 options are available to the investigator as subjects transition from the screening period to the Abilify MyCite treatment (prospective) phase:

- 1) Antipsychotic medications other than oral aripiprazole may be tapered off and/or discontinued during the screening period prior to the subject receiving the first treatment with Abilify MyCite.
- 2) Antipsychotic medications other than oral aripiprazole may be continued during the screening period and cross-titration with oral aripiprazole trial drug may occur. Some investigators may choose this option for the subject depending as local practice patterns dictate and on the subject's safety.

Abilify MyCite treatment (prospective) phase

For subjects enrolled in the trial, those not on aripiprazole at screening and who need to cross-titrate will do so during the screening period for conversion to aripiprazole from other antipsychotics according to the approved labels. At the baseline visit (Day 1), Abilify MyCite onboarding will be provided with informational materials and additional call center support. Initiation of Abilify MyCite treatment will commence at the baseline (Day 1) visit, with subjects ingesting the Abilify MyCite tablet embedded with an IEM sensor product, wearing the patch, and using the smartphone app for up to 6 months, including a required 3 months (Months 1 to 3) of Abilify MyCite treatment. This will be followed, at investigator discretion, to either change to oral standard-of-care antipsychotic treatment (eg, oral or LAI) or remain on Abilify MyCite for the second 3-month period (Months 4 to 6), during the prospective phase. The first dose of Abilify MyCite is to be taken at the baseline (Day 1) visit (in the clinic) during onboarding, unless they have already taken their daily dose. Subjects should not take their oral standard-of-care medication that morning before the baseline (Day 1) visit.

During the assessment period, subjects will visit the investigator for clinical evaluations at baseline (Day 1), Month 3, and Month 6/early termination (ET). Monthly assessments

Protocol 31-201-301 Interim Analysis Plan

will follow a 28-day schedule, and at each visit and at any unscheduled visits, the subject's clinical status will be evaluated. All hospitalizations and all interventions (psychiatric only as well as pharmacy cost of all medications) will be recorded, in addition to all other assessments outlined in this protocol. The primary endpoint will be assessed at Month 3. The final trial visit will be on Month 6/ET and will be followed by a 30-day (- 3/ + 2 day) safety follow-up period for subjects continuing on Abilify MyCite. For subjects completing Months 4 to 6 on standard of care, a 30-day safety follow-up period is not required. Subjects will also visit the clinic for medication dispensing and accountability at the scheduled visits. Any treatment changes, including reason for the change, will be recorded in the electronic case report form (eCRF).

Evaluation of safety and tolerability of Abilify MyCite as assessed by frequency and severity of the AEs to be collected in this trial, i.e., serious AEs (SAEs), nonserious AEs, potential hepatotoxicity cases, and pregnancies.

Subject use of the Abilify MyCite system can be monitored by their respective investigators, who are suggested to review the physician dashboard data at a minimum of every 2 weeks and make changes to current treatment plan and therapy at their discretion. The investigators may request that a subject return to the site for unscheduled visits as deemed appropriate. In the event of an unscheduled visit, review of the investigator dashboard and safety events will be collected.

Safety follow-up

All subjects who complete or withdraw from the trial while on Abilify MyCite (unless they have withdrawn their consent for participation in the trial) will receive a telephone call for safety follow-up at 30 days (- 3/ + 2 days) after the last trial visit.

This telephone contact will be made to assess if there were any AEs experienced since the last trial visit. In addition, the subject will be asked about any new medications or changes in existing medications and the information will be documented. The trial design is presented in [Figure 3.1 1](#).

Protocol 31-201-301 Interim Analysis Plan

[figure not shown]

Figure 0-1 Trial Design Schematic

Note: Monthly assessments will follow a 28-day schedule.

3.2 Trial Treatment

The subjects will receive Abilify MyCite as prescribed by their investigators. The subject and the investigator will initiate the system at the baseline (Day 1) visit and use it for up to 6 months, including a required 3 months (Months 1 to 3) of Abilify MyCite treatment. This will be followed, at investigator discretion, to either change to standard-of-care antipsychotic treatment (eg, oral or LAI) or remain on Abilify MyCite for the second 3-month period (Months 4 to 6) during the prospective phase.

3.3 Study Population

The study population will include male and female subjects, 18 to 65 years of age, inclusive, with a diagnosis of schizophrenia according to DSM-5 criteria. Subjects must have had at least 1 inpatient psychiatric hospitalization within the 4 years (48 months) prior to screening but must not have been hospitalized for any psychiatric reason during the 4 weeks prior to signing the ICF or at any time during the screening period. Subjects must have been on oral antipsychotics treatment in the last 7 months prior to screening.

4 Sample Size and Power Justification

The primary endpoint of this trial compares the paired proportions of inpatient psychiatric hospitalization during the retrospective period (Month 1 to 3) and the prospective period (Month 1 to 3), which will be analyzed using a McNemar test.

Based on published results of other similar studies for the particular time periods

Protocol 31-201-301 Interim Analysis Plan

(retrospective Month 1 to 3 and prospective Month 1 to 3) we are evaluating, it is reasonable to assume that 15.5% of the subjects are hospitalized during retrospective Month 1 to 3 and 7% are hospitalized during prospective Month 1 to 3; about 5% of subjects who are not hospitalized retrospective will be hospitalized prospectively, while 13.5% of the subjects who are hospitalized retrospectively will not be hospitalized. With this assumption, 200 completed subjects will provide 80% power ($\alpha = 0.05$ two-sided) to detect a difference of 8.5% in the paired hospitalization proportions between pre-switch and post-switch periods while the proportion of total discordant pairs is 18.5%. In addition, this sample size will provide 80% power for the comparison of retrospective Month 4 to 6 vs prospective Month 4 to 6, assuming 30% of the subjects are hospitalized pre-switch (12.5% subjects will be hospitalized post-switch and another 17.5% won't have hospitalization post-switch) and, overall, 20% are hospitalized post-switch (among them, 12.5% subjects are hospitalized both pre-switch and post-switch and 7.5% have no hospitalization pre-switch).

Two interim analyses are planned at when 50% and 70% of subjects have completed the prospective period (Month 1 to 3); in order to conserve the overall Type I error at 0.05 level, 224 to 300 evaluable subjects are needed to complete the 3-month treatment to maintain 80% power. This sample size assumes the 3 sequential tests are made using LanDeMets Spending Function with O'Brien-Fleming boundary, a futility conditional power of 15% is built in the sample size calculation to allow the trial to stop for futility. Based on the conditional power and the alpha level at the interim analysis, the trial could stop for efficacy or futility, continue with the initially planned 224 sample size or increase to up to 300 if the conditional power fall between 50% to 80% (Section 4.7). The 2-sided alpha levels for these 2 interim analyses are 0.00312 and 0.0139 respectively, and the alpha left for the final analysis will be 0.04528.

5 Statistical Analysis Dataset

5.1 Data/Data Sets Specifications

5.1.1 Data Sets Analyzed

The following analysis samples are defined for this study:

Enrolled Sample: comprises all subjects who sign an eICF for the trial and entered screening.

Safety Sample: comprises all subjects who receive at least one dose of study medication in the prospective phase.

Protocol 31-201-301 Interim Analysis Plan

Intent-to-Treat Sample: consists of all Enrolled Sample who met the study inclusion/exclusion criteria and who are intended to receive study medication in the prospective phase.

Modified Intent-to-Treat (mITT): dataset which will consist all ITT subjects entering the prospective phase who have taken at least 80% of the study medication for the specified analysis period, and had complete information on hospitalization during the specified analysis period; that is for the Month 1-3 mITT: the specified period will be Month 1-3 prospective/respective; for the Month 4-6 mITT and Month 1-6 mITT, the specified period will be Month 4-6 prospective/respective and Month 1-6 prospective/respective, respectively.

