3.12 Subject Compliance

Subjects will be required to have at least 3 months of Abilify MyCite medication. Noncompliant subjects will be followed throughout the trial period and analysis will be performed as described in [Section 7.4](#). Discontinuation of noncompliant subjects is at the discretion of the investigator.

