7.2 Datasets for Analysis

The safety dataset includes all subjects that were administered at least one dose of Abilify MyCite.

The following analysis samples are defined for this trial:

- Enrolled Sample: comprises all subjects who sign an eICF for the trial.
- Prospective Safety Sample: comprises all subjects who receive at least one dose of Abilify MyCite in the prospective phase.
- Efficacy Sample: the core dataset for all efficacy analyses is the modified Intent-to-Treat (mITT) dataset which will consist of data from all subjects entering the prospective phase who have completed the first 3-months of dosing on Abilify MyCite. However, as will be described below, in order to handle missing data and restrictions imposed by different types of analyses (eg, change from baseline analysis), other datasets derived from the ITT dataset will be used for the efficacy analyses.

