7.3 Handling of Missing Data

For the primary variable, the analysis will be based on the proportion of days with good patch coverage during the trial and no imputation will be performed for missing data. For analysis of change from baseline (Day 1), last-observation-carried-forward (LOCF) and observed-cases (OC) methods will be used, as considered applicable. No imputation will be performed for other missing data, unless specified otherwise.

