7.1 Primary Efficacy Analysis Endpoint

The primary endpoint of this trial is the comparison of inpatient psychiatric hospitalization rates (proportion of subjects with ≥ 1 inpatient psychiatric hospitalization[s]) between the retrospective period (Months 1 to 3) while on oral standard-of-care antipsychotic treatment and the prospective period (Months 1 to 3) after the switch to Abilify MyCite. Primary analysis will use the mITT for Month 1 to 3.

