7.1.1 Statistical Methods of Primary Efficacy Analysis

The primary analysis will be achieved by testing for statistically significant (at 2-sided overall alpha = 0.05). The analysis will be performed using a McNemar test on those who have hospitalization data during Months 1 to 3 prior to the screening period and during Months 1 to 3 after switch to Abilify MyCite.

Protocol 31-201-301 Interim Analysis Plan

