2.2 Interim Efficacy Analysis

The purpose of the interim analyses is to decide whether there is sufficient evidence that the study will be stopped to declare efficacy or futility, or addition subjects are needed to have sufficient power to achieve the primary objective.

The primary endpoint of this trial is the comparison of inpatient psychiatric hospitalization rates (proportion of subjects with ≥ 1 inpatient psychiatric hospitalization[s]) between the retrospective period (Months 1 to 3) while on oral standard-of-care antipsychotic treatment and the prospective period (Months 1 to 3) after the switch to Abilify MyCite.

The analysis on the primary endpoint will be performed using a McNemar test, those who have hospitalization data during Months 1 to 3 prior to the screening period and during Months 1 to 3 after switch to Abilify MyCite for the modified Intent-to-Treat (mITT) sample; this will be a 2-sided test.

Two interim analysis are planned when 50% and 70% of subjects have completed the prospective phase (3 months). At the end of the interim analysis, a decision will be made to continue with/without sample size increase, stop for efficacy or stop for futility based on the p-value and conditional power from the interim data (as described in [Table 2-1](#)). Subjects will continue to be enrolled into the trial during the interim analysis; if the trial is stopped due to futility, all randomized subjects will be terminated; however, if the interim analysis stops the trial for efficacy, then all randomized subjects will continue until the last observation. Subjects in screening will be discontinued and no further randomization will occur. The 2-sided alpha levels for these 2 interim analyses are 0.00312 and 0.0139 respectively, and the alpha left for the final analysis will be 0.04528. The sample size will be re-estimated only based on the conditional power determined at the interim analysis. The adaptive designs methodology published by Chen, Dements and Lan (2004) will be used to increase the sample size based on the estimate of the treatment effect size of the primary efficacy endpoint at interim, possibly combined with other external information, without inflating the Type I error. Should the timing or frequency of the interim analysis be different from the previously specified, stopping boundary would be re-calculated using the alpha spending function.

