2.2.1 Data Set Analyzed

The following analysis samples are defined for this study:

Enrolled Sample: comprises all subjects who sign an E-informed consent form (eICF) for the trial.

Safety Sample: comprises all subjects who receive at least one dose of study medication in the prospective phase.

Intent-to-Treat Sample: consists of all Enrolled Sample who met the study inclusion/exclusion criteria and who are intended to receive study medication in the prospective phase.

Modified Intent-to-Treat (mITT): dataset which will consist all ITT subjects entering the prospective phase who have taken at least 80% of the study medication for the specified analysis period, and had complete information on hospitalization during the specified analysis period; that is for the Month 1-3 analysis: the specified period will be Month 1-3 prospective/respective; for the Month 4-6 mITT and Month 1-6 mITT, the specified period will be Month 4-6 prospective/respective and Month 1-6 prospective/respective, respectively.

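### The primary and interim McNemar tests keep only subjects who took at least 80% of study medication in prospective Months 1–3, a post-baseline filter that can remove prospectively hospitalised subjects and has no retrospective counterpart

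*SAP*

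**What the plan says.** SAP 7.1 states "Primary analysis will use the mITT for Month 1 to 3". SAP 5.1.1 limits that set to ITT members who start prospective treatment and meet two conditions: "who have taken at least 80% of the study medication for the specified analysis period, and had complete information on hospitalization". The Interim Analysis Plan bound with the SAP repeats the rule in its Section 2.2.1 ("dataset which will consist all ITT subjects entering the prospective phase who have taken at least 80% of the study medication"). Its Section 2.2 runs the interim McNemar test on the same set, using data "after switch to Abilify MyCite for the modified Intent-to-Treat (mITT) sample". Neither text says how intake is measured or how days spent as an inpatient count.

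Other passages describe different populations for the same test:

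- **SAP 7.1.1 and Protocol 7.4.1** set no adherence condition. The analysis is "using a McNemar test on those who have hospitalization data during Months 1 to 3 prior to the screening period" and during the matching prospective months.
- **Protocol 3.12** says "Noncompliant subjects will be followed throughout the trial period" and refers to Section 7.4 for their analysis. SAP 5.1.1 removes them.
- **Protocol 7.2** builds efficacy on "subjects entering the prospective phase who have completed the first 3-months of dosing on Abilify MyCite". This is a different filter, but also a post-baseline one.
- **Protocol 7.3** says of the primary variable that "the analysis will be based on the proportion of days with good patch coverage during the trial". That cannot apply to a hospitalisation endpoint.

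The only sensitivity analysis described (SAP 7.1.3, Interim Analysis Plan 2.2.2) narrows the mITT further, to 3-month completers. SAP Appendix 2 lists an ITT version of the primary table (CT-5.1.2) and an ITT hospitalisation listing (EFF-1.3), with no stated role or missing-data rule. The interim table list has no ITT hospitalisation table.

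**The concern.** Study medication starts on Day 1, so the 80% rule can act only on the prospective side. For the retrospective period, Protocol 3.1 asks only for evidence of prescription. Intake and prospective admissions share one 84-day window (SAP 7.1.2), so the outcome can help decide who is analysed. A subject who relapses, misses doses or stops MyCite, and is admitted, can leave the test. A subject hospitalised only in the retrospective period meets no such hurdle.

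McNemar's test uses only the discordant pairs. Losing subjects hospitalised only prospectively, faster than subjects hospitalised only retrospectively, moves the result towards MyCite. There is no control arm to reveal this. A significant final result, or an early stop for efficacy at 0.00312 or 0.0139, could then partly reflect who was retained. The described sensitivity analysis is a subset of the filtered set and cannot detect it.

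**Working it through.** **1. The plan's own figures.** Inputs from Protocol 7.1: hospitalised only retrospectively p10 = 13.5%; only prospectively p01 = 5%; two-sided alpha 0.05; 80% power.

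N = [1.96·√0.185 + 0.842·√(0.185 − 0.085²)]² / 0.085² = 198.6, so 199 (stated: 200). Power at 200 is 80.3%. A three-look simulation at the stated alphas, with futility below 15% conditional power, gives 80.2% at 224. The sample-size arithmetic is sound; the problem is the analysis set.

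**2. The threshold.** 0.80 × 84 = 67.2. With one dose due daily and all 84 days in the denominator, 68 doses keep a subject in and 17 missed doses put one out.

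**3. Effect on the error rate.** Retention by hospitalisation status is not documented, so it is varied.

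- Enrolled 320, analysed 224 (Protocol 3.3), so 30% are excluded overall.
- 2% hospitalised in both periods (15.5 − 13.5 = 7 − 5 = 2).
- No true effect: p10 = p01 = d, with d = 5%, 9.25% (half of 18.5%) or 13.5%.
- Exclusion e among prospectively hospitalised subjects. Exclusion x among all others is set by 0.30 = (d + 0.02)·e + (1 − d − 0.02)·x.
- Uncorrected McNemar z > 1.96 favouring MyCite (nominal 2.5%); 200,000 simulated trials per cell.

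One cell by hand, d = 9.25% and e = 50%: x = (0.30 − 0.1125 × 0.5)/0.8875 = 0.275. Expected pairs kept are 320 × 0.0925 × 0.725 = 21.5 retrospective-only and 320 × 0.0925 × 0.5 = 14.8 prospective-only. The mean z is about 6.7/√36.3 = 1.11, so the chance of passing 1.96 is about 20% (simulated 19.4%).

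| e | d = 5% | d = 9.25% | d = 13.5% |
|---|---|---|---|
| 30% | 2.7% | 2.5% | 2.4% |
| 40% | 5.9% | 7.7% | 9.9% |
| 50% | 12.0% | 19.4% | 28.6% |
| 60% | 22.9% | 41.1% | 58.9% |
| 70% | 39.8% | 69.0% | 86.6% |

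At e = 30%, exclusion is unrelated to admission and there is no bias.

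**4. Offset.** If retrospective-only subjects are also lost more often, the bias shrinks. Prospective-only 50% and retrospective-only 40% gives 5.8%, 7.5% and 9.0% across the three nulls; 50% for both gives 2.4–2.6%.

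**5. Smaller loss to the filter.** If the filter removes only 5–15% of 320 subjects (d = 9.25%), a 10-point exclusion gap gives about 6% and a 20-point gap about 12–14%.

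**6. With the interims.** In a separate three-look calculation at 224, prospectively hospitalised subjects are retained at 0.8 or 0.5 times the rate of the others. Two-sided rejection of a true null is about 7–13% or 27–65%, almost all favouring MyCite.

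**7. Tipping counts at the planned effect.** 224 × 13.5% ≈ 30 and 224 × 5% ≈ 11; χ² = 19²/41 = 8.80, p = 0.003. Now add pairs from the 96 excluded subjects (320 − 224):

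- No retrospective-only pairs: 5 prospective-only gives 30 vs 16, p = 0.039; 6 gives 30 vs 17, p = 0.058.
- The planned 13.5% (13) retrospective-only pairs: 15 prospective-only gives 43 vs 26, p = 0.041; 16 gives 43 vs 27, p = 0.056.

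**The case against.** **The route from admission to exclusion is not written down.** Protocol 5.1 makes inpatient hospitalisation an SAE criterion, but also says the reason for admission, not the admission itself, should be reported. Section 5.2 limits when an exacerbation counts as an AE. The rule withdrawing subjects who need psychiatric admission sits in the cross-titration section (3.2.1). No passage says a prospective admission stops MyCite or counts as missed doses, and a short or late stay may not breach 80%. This stands, and is why the claim is that the filter can remove such subjects. Missed doses around a relapse, and stopping MyCite for a required disallowed medication (3.8.3.1), remain plausible routes.

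**The 17-dose cut-off depends on an undefined denominator.** SAP 8.2.2 leaves out doses missed through premature discontinuation from the study. That section describes a separate compliance summary, though, and 5.1.1 does not adopt its convention. The gap is itself a fault.

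**The 320-to-224 gap is planned non-completion, not loss to the 80% rule.** Fair: the table in step 3 measures all exclusion together, and subjects with no hospitalisation status would be missing under any set. Step 5 shows that inflation persists when the filter takes a much smaller share. The second tipping count also needs 16 of 96 (16.7%) prospective-only admissions, over three times the planned 5%, and the 60–70% rows have no support in the documents.

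**Retrospective selection exists too.** Exclusion criterion 4 bars anyone given an LAI in the retrospective phase, which could work against MyCite. This makes the net direction for the whole trial less certain, but it does not correct the filter.

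**The ITT table would expose the problem, and on-treatment effect is a legitimate question.** The table helps at the final analysis only, with no role attached. An adherent-subject question can be asked as a supportive analysis; as the primary test it conflicts with SAP 7.1.1 and Protocol 7.4.1.

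**Conclusion.** The concern holds and should be fixed before the first interim. An undefined adherence filter, measured over the same window as the outcome and on one side of the mirror only, governs the primary test and both interim decisions. It contradicts the plan's own description of who is tested.

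The direction favours MyCite if prospectively hospitalised subjects are excluded more often than retrospectively hospitalised ones; if not, there is no such bias. Under the stated assumptions, a 2.5% one-direction error becomes 6–10% at 40% exclusion of prospectively hospitalised subjects and 12–29% at 50%. The actual size cannot be known from the documents.

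**What to change.** - In SAP 5.1.1 and 7.1, the Interim Analysis Plan (2.2, 2.2.1) and Protocol 7.2, define the primary set as all subjects dosed at least once who have Months 1–3 hospitalisation status in both periods, regardless of adherence or MyCite discontinuation. Use it at both interims and the final analysis.
- Keep the 80% mITT and the 3-month completers as supportive sets. State how intake is measured, its denominator, and how inpatient days count.
- Add a worst-case or tipping-point analysis for dosed subjects with incomplete Months 1–3 follow-up.
- Delete the patch-coverage sentence for the primary variable in Protocol 7.3.
- Add the matching hospitalisation table to the interim table list.

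**Cost.** Wording changes and revised table shells. No new data type is needed: Protocol 3.8.3.1 and 3.12 already intend follow-up after stopping or noncompliance, and EFF-1.3 already lists ITT hospitalisations.

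The real price is possible dilution. If 30% of subjects get no benefit, the difference is 0.7 × 8.5 = 5.95 points. With q discordant each way in that 30%, p10 = 0.7 × 13.5% + 0.3q and p01 = 0.7 × 5% + 0.3q. Fixed-sample power with 320, ignoring the interims, is 64% for q = 13.5% (13.5%/7.55%), 70% for q = 9.25% (12.225%/6.275%) and 76% for q = 5% (10.95%/5%). If the extra 96 subjects follow the planned rates, power is 95%. The stated power should be redone for the new set.
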